5.1.1. Screening and Baseline Periods

The Screening Period is from 7 up to 42 days prior to baseline. At screening, the parent or legal guardian will sign the informed consent form (ICF) and the participant will sign the assent form (as appropriate) per local requirements prior to any study assessments, examinations, or procedures being performed ([Appendix 3](#)). All screening procedures will be performed according to the Schedule of Activities (Section [2](#)).

The preferred TB test is QuantiFERON® TB Gold test. In countries where the QuantiFERON®- TB Gold test is not available or due to investigator's judgement (e.g., need to reduce the volume of blood collected), T-spot or the purified protein derivative (PPD) test may be used. In the case of selecting the PPD test, the participant must return within 48 to 72 hours to read the skin test. The PPD test result does not need to be read at the site, but must be assessed by a trained healthcare professional, and documented results provided to the site as soon as possible.

Treatment with concomitant JIA therapies and topical corticosteroids during the study is permitted only as described in Section [7.7](#). Participants will remain on background MTX, other csDMARDs and oral, topical or ophthalmic corticosteroids if participants are on stable doses of these treatments at screening (see Sections [6.2](#) and [7.7](#). for details).

Participants with a positive HCV antibody will return to the site and have an HCV RNA sample drawn, which will be processed centrally. Results must be known prior to enrollment. Participants who are positive for HCV antibody and negative for HCV RNA may be enrolled.

Participants with a positive hepatitis B core antibody (HBcAb) will return to the site and have an HBV DNA sample drawn, which will be processed centrally. Results must be known prior to enrollment. Any enrolled participant who is HBcAb positive, regardless of hepatitis B surface antibody (HBsAb) status or level, must undergo HBV DNA testing per the Schedule of Activities (Section [2](#)).

Pregnancy tests will be given prior to the first dose of investigational product for females ≥ 10 years of age (< 10 years at investigator discretion) if menarche has been reached or if there is reason to believe the participant is sexually active. Pregnancy test results from baseline must be known prior to first dose of investigational product.

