6.4. Screen Failures

Screen failures are defined as participants who consent to participate in the clinical study but are not subsequently entered in the study. A minimal set of screen failure information is required to ensure transparent reporting of screen failure participants to meet the Consolidated Standards of Reporting Trials (CONSORT) publishing requirements and to respond to queries from regulatory authorities. Minimal information includes demography, screen failure details,

eligibility criteria, and any SAE.

Individuals who do not meet the criteria for participation in this study (screen failure) may be re-screened. Re-screened participants should be assigned a new participant number. When re-screening, the screening tests and procedures should be repeated. Those who test positive for latent TB at screening or who have a documented history of a positive TB test but no documented history of at least 4 weeks of appropriate latent TB treatment, may be re-screened following appropriate treatment. Other reasons for re-screening must be discussed, approved, and documented by the Lilly Medical Team (Clinical Research Scientist [CRS]/Clinical Research Physician).

Individuals may be rescreened 1 time. The interval between rescreenings should be at least 4 weeks. Individuals who are to be rescreened must first sign a new ICF/assent form as applicable ([Appendix 3](#)). Such individuals will be assigned a new participant number.

7. Treatments

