Changes in study conduct not described in this appendix, or not consistent with applicable local regulations, are not allowed. The following changes in study conduct will not be considered protocol deviations.

1. Remote Visits

In source documents and the CRF, the study site should capture the visit location and method, with a specific explanation for any data missing because of missed in-person site visits.

Telemedicine: Telephone or technology-assisted virtual visits, or both, are acceptable to complete appropriate assessments. Assessments to be completed in this manner include, but are not limited to,

- Immunization record
- AEs and product complaints
- Concomitant medications
- Clinician reported measures except for those assessments or fields that require joint manipulation, such as Joint Assessment, Enthesitis Assessment, Dactylitic Count, Physician's Global Assessment of Disease Activity, and Clinical Sacroiliitis
- Participant/Parent administered measures

Other alternative locations: Other procedures that may be done at an alternate location in exceptional circumstances are local draw labs, investigational product preparation and administration. This alternative location may count as an “on-site” visit with regard to the guidance in this appendix.

In the event that access to the site is not possible, and with approval from Lilly Medical, sites will follow the guidance in the table below.

Visit(s)	Guidance
V1-V2	If one of these visits cannot be accomplished at the site, then the visit should be postponed. Refer to Section “Screening Period Guidance” in this appendix for further screening guideline and Section “Adjustments to Visit Windows” in this appendix for visit window adjustments.
V7	This visit must be performed at site (Primary Outcome).

	Participants under Ixekizumab Arm	Participants under Adalimumab Arm
OLT Visits (V3-V6)	Use a combination of telephone/telemedicine with use of an acceptable alternative site for the safe administration of the ixekizumab injection and assessments performed by site personnel.	Use a combination of telephone/telemedicine with use of an acceptable alternative site for assessments performed by site personnel.

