In addition, if study intervention will be administered to the participant at an alternate location, these additional requirements must be met:

- Only authorized study personnel may supply, prepare, or administer study intervention.
- Requirements and instructions for investigational product storage and dose preparation will be the same as stated in main protocol,

Pharmacy Binder and Ixekizumab Dosing Instructions Manual must be followed.

4. Screening Period Guidance

To ensure safety of study participants, laboratory values, and other eligibility assessments taken at screening visit are valid for a maximum of 42 days. The following rules will be applied for active, nonrandomized participants whose participation in the study must be paused due to exceptional circumstances:

- If paused for less than 42 days from screening to randomization visit: The participant will proceed to the next study visit per the usual Schedule of Activities, provided that randomization visit must be conducted within 7 days from first screening.
 - The site should conduct the next visit if the participant's eligibility criteria are confirmed, and the site should document the reason for delay in the CRF.
 - Due to the pause in screening, sites should also reconfirm the impacted participant's consent and document this confirmation in the source documentation.
- If paused for more than 42 days from screening to randomization visit: The participant must be discontinued because of screening interruption due to an exceptional circumstance. This is documented as a screen fail in the CRF with a reason of exceptional circumstance. This screen fail is allowed in addition to the main protocol screen fail. The participant can reconsent and be rescreened as a new participant. The screening procedures per the usual Schedule of Activities should be followed, starting at screening visit to ensure participant eligibility by randomization visit.

5. Adjustments to Visit Windows

Whenever possible and safe to do so, as determined by the investigator's discretion, participants should complete the usual Schedule of Activities. To maximize the possibility that these visits can be conducted as on-site visits, the windows for visits may be adjusted, upon further guidance from the sponsor. This minimizes missing data and preserves the intended conduct of the study.

This table describes the allowed adjustments to visit windows.

Visit Number	Tolerance

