5.1. Summary of Study Design

Study I1F-MC-RHCG (RHCG) is a multicentre, randomized, open-label study of subcutaneous (SC) ixekizumab, with adalimumab as a reference arm in children from 2 to less than 18 years of age, who are biologic disease-modifying antirheumatic drug- (bDMARD-) naive or inadequate responder (bDMARD-IR) as per investigator's judgement, with JIA subtypes of ERA (including juvenile-onset ankylosing spondylitis [JoAS]) and juvenile psoriatic arthritis (JPsA).

The study consists of 5 periods:

- **Screening Period** (Visit 1) will assess subject eligibility and will occur approximately 7 to 42 days before the Open-Label Treatment (OLT) Period (baseline; Week 0; Visit 2).
- **Open-Label Treatment Period** (OLT) will occur from Week 0 (baseline; Visit 2) to Week 16 (Visit 7). **CCI**
Evaluation of the primary endpoint will occur at Week 16.
- **Open-Label Extension Period** (OLE) will occur from Week 16 (Visit 7) to Week 104 (Visit 29/ Early Termination Visit [ETV]). All patients who were receiving ixekizumab in the OLT period will continue to receive ixekizumab for approximately 88 weeks during the OLE Period. Patients receiving adalimumab during the OLT period who did NOT attain a JIA ACR30 response at Week 16 will be switched to ixekizumab in the OLE period. Patients receiving adalimumab during the OLT period who did attain a JIA ACR30 response at Week 16 will be given the option to switch or not to switch to ixekizumab at any visit during the OLE period. The decision to switch for adalimumab-treated patients who achieved a JIA ACR30 response at Week 16 will be left to the patient/patient's caregiver and investigator. After switching to ixekizumab, the patients will not have the option to resume adalimumab treatment during the remainder of the trial participation.
- **Long-Term Extension Period** (LTE): Participants who complete the OLT and OLE periods will be participating in the LTE period of this study which will occur from Week 104 (Visit 29) to Week 264 (Visit 69/ ETV). All participants entering the LTE portion of the study period will receive weight-based ixekizumab at Week 104. Participants who were previously assigned to adalimumab will be switched to ixekizumab as described in Section 7.1 Treatments Administered of the protocol. If a participant previously assigned to adalimumab does not want to switch to ixekizumab in the LTE period of the study, the patient should initiate the ETV process at Week 104.

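### Protocol Appendix 8 requires a paused participant to be randomised within 7 days of first screening, which turns the 7-day minimum of the screening window into a maximum and conflicts with the 42-day validity limit in the same section

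*Protocol*

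**What the plan says.** Appendix 8, section 4 begins from the premise that laboratory values and other eligibility assessments "taken at screening visit are valid for a maximum of 42 days". Two branches follow for participants who are not yet randomised and whose participation has to be paused.

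- **Paused for less than 42 days.** The participant goes on to the next visit under the usual Schedule of Activities, "provided that randomization visit must be conducted within 7 days from first screening". The site confirms eligibility, reconfirms consent and records why the visit was late.
- **Paused for more than 42 days.** The participant is discontinued as a screen failure and may reconsent and be rescreened. "This screen fail is allowed in addition to the main protocol screen fail".

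The ordinary screening window is stated consistently elsewhere. Section 5.1.1: "The Screening Period is from 7 up to 42 days prior to baseline". SAP Section 5.1: screening "will occur approximately 7 to 42 days before the Open-Label Treatment (OLT) Period". The screening column of Table RHCG.2.1 runs from day −42 to day −7. Randomisation takes place at Visit 2, which is baseline (Section 7.2).

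Two other parts of Appendix 8 bear on this. For Visits 1 and 2, the remote-visit table says: "If one of these visits cannot be accomplished at the site, then the visit should be postponed". The table of adjusted visit windows starts at Visit 3, so it gives no separate allowance for the interval from screening to randomisation.

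**The concern.** In the normal schedule 7 days is a floor. The proviso makes it a ceiling, in a sentence that also tells the site to follow the normal schedule and inside a branch that is meant to run to almost 42 days. A site holding valid results for a child on, say, day 20 is told to proceed and, by the same sentence, not to.

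The site cannot simply pick the sensible reading with full cover. The rules in section 4 are written as rules to be applied, and Appendix 8 disallows changes in conduct that it does not describe and exempts only those it does describe from being protocol deviations. A site that randomises on day 20 acts reasonably but against the wording. A site that follows the wording has a child with valid results and no stated next step.

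What could follow is a rescreen under Section 6.4, with new consent or assent: "When re-screening, the screening tests and procedures should be repeated". That section also limits how often this can happen: "Individuals may be rescreened 1 time. The interval between rescreenings should be at least 4 weeks". In a paediatric trial with blood-volume limits, a needless repeat of Visit 1 is worth avoiding.

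**Working it through.** No power, alpha or sample size figure is involved. The check is a count of whole days, *d*, from first screening to randomisation. It assumes that the pause in the two branch conditions is measured over that same interval, as their wording indicates.

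**Inputs**

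| Rule | Source | Days |
|---|---|---|
| Screening window | Protocol Table RHCG.2.1 and 5.1.1; SAP 5.1 | 7 ≤ *d* ≤ 42 |
| Validity of screening results | Appendix 8, section 4 | *d* ≤ 42 |
| Proceed branch, condition | Appendix 8, section 4 | *d* < 42 |
| Proceed branch, proviso | Appendix 8, section 4 | *d* ≤ 7 |
| Screen-failure branch, condition | Appendix 8, section 4 | *d* > 42 |

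**Counts**

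1. Days in the screening window: 42 − 7 + 1 = 36.
2. Days in the window that also meet the proviso: 7 ≤ *d* ≤ 7, so day 7 only. That is 1 of 36. Days 0 to 6 would meet the proviso but fall short of the window's minimum.
3. Days in the window that meet the proceed condition: 41 − 7 + 1 = 35.
4. Of those, days that fail the proviso: 41 − 8 + 1 = 34 (days 8 to 41). They are not in the screen-failure branch either, so no disposition is stated.
5. Day 42 is neither less than 42 nor more than 42, so it falls in no branch, although results are still valid on that day.
6. With the limits set at 7 ≤ *d* ≤ 42 and branches at *d* ≤ 42 and *d* > 42, all 36 days are usable and every day has a disposition.

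These are calendar days, not participants. The number of children affected cannot be derived from the documents.

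**If a site did rescreen.** The repeat Visit 1 blood draw follows from Appendix 7 (chemistry, haematology, hepatitis B/C, HIV). For ages 2 to under 8 it is 4.7 + 1.2 + 4.7 + 1.1 = 11.7 mL. For ages 8 and older with a repeat QuantiFERON it is 11.7 + 4.0 = 15.7 mL; if a negative TB result from the previous 3 months is accepted (Section 9.4.6), it stays at 11.7 mL. This prices one possible outcome, not one the text prescribes.

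**The case against.** The best case on the other side is that this is one misworded clause and that its neighbours show what was meant. Results are valid to 42 days. The same sentence points to the usual Schedule of Activities, which already sets both limits. The site is told to record the reason for delay, and a participant randomised on day 7, the earliest permitted day, has no delay to explain. Visits 1 and 2 are to be postponed when the site cannot be reached, which lengthens the interval. Discontinuation is required only beyond 42 days. All of this stands, and it makes the intended rule largely clear. It also counts against reading the 7 days as a deliberate tightening, since the 42-day branches would then have almost no purpose. But a reader reaches the sensible rule only by discarding an explicit condition on randomisation, which is a reason to correct it.

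Two stronger readings are tempting, and the documents do not support them.

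- *Children at days 8 to 41 are forced into a rescreen.* The text gives them no disposition. Apart from the latent-TB route, Section 6.4 requires reasons for rescreening to be discussed with and approved by the sponsor's medical team, so an unnecessary rescreen would probably be caught. The 4-week interval is not necessarily a fresh wait: counted from first screening, it has already passed for days 28 to 41, which is 41 − 28 + 1 = 14 of the 34 days.
- *A child with valid results is treated worse than one whose results have expired.* The extra screen-failure allowance does appear only in the more-than-42-day branch. The comparison still depends on the same unwritten rescreen step, and the participant in that branch must also reconsent and repeat screening.

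**Conclusion.** The point holds as an internal inconsistency: the operative threshold in a rule about when a participant may be randomised is wrong as written. Only 1 of 36 permitted days meets both rules, 34 days are told to proceed yet fail the proviso, and day 42 belongs to neither branch. The overlap is not empty, and a 7-day limit does not by itself contradict a 42-day validity limit. The conflict arises because it empties the under-42-day branch and reverses the 7-day minimum.

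The reach is small. Appendix 8 applies only in exceptional circumstances and with the sponsor's written approval, and the sponsor can add written guidance. A repeat consent, repeat tests and a further blood draw are possible consequences, not stated ones. The documents do not show whether screening was still open under this version. A reader might also suspect an effect on the trial's results. There is none: the SAP does not use the Appendix 8 rule, and no analysis, sample size or primary conclusion changes.

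**What to change.** Replace the proviso with wording such as: *provided that the randomization visit takes place at least 7 and no more than 42 days after first screening*. Deleting it would also work, since the Schedule of Activities already sets both limits. In either case, label the two branches as 42 days or less and more than 42 days, so that day 42 has a home.

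The cost is one clause and two labels in one appendix, with no new procedures. It can go into the next amendment and, until then, be clarified in the additional written guidance that Appendix 8 already allows the sponsor to issue.

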Appendix 9. Protocol Amendment History

The Protocol Amendment Summary of Changes Table for the current amendment is located directly before the Table of Contents (TOC).

Amendment [b]: (21-Sep-2022)

This amendment is considered to be substantial.

The amendment is considered to be substantial because it is likely to have a significant impact on the

- safety or the rights of the study participants
- reliability and robustness of the data generated in the clinical study

Overall Rationale for the Amendment:

To include Long Term Extension Study information to determine long term efficacy and safety of LY2439821 in children with Juvenile Idiopathic Arthritis Subtypes of Enthesitis-related Arthritis (Including Juvenile-Onset Ankylosing Spondylitis) and Juvenile Psoriatic Arthritis.

Section # and Name	Description of Change	Brief Rationale
Title Page	
 ● Adjusted to follow the harmonized template. ● Deleted original title page. 	For alignment of Legacy Protocol documents with the new harmonized template.
SOC Table	Protocol Amendment SOC table added.	For alignment with new harmonized template.
Section 1. Synopsis	LTE period data added.	For alignment.
Section 2. Schedule of Activities	
 ● LTE tables added, and OLE adjusted. ● Visit and week numbering adjusted. ● Weight recording adjusted to 10th of a kilogram. ● Deleted the Self-Harm Follow-up Form ● Specified that the Global Assessment of Well-Being must be completed by a caregiver until participant ≥ 14 years of age. 	For alignment and accuracy.

Section # and Name	Description of Change	Brief Rationale
Section 3.1 Study Rationale	Study Rationale for LTE period information added.	For accuracy.
Section 3.2 Background	IXORA-PEDS trial information added.	For alignment.
Section 4 Objectives and Endpoints	LTE O/E added.	For accuracy.
Section 5.1 Overall Design	
 • LTE information added. • LTE treatment period added. • Schema Adjusted to incorporate LTE information. 	For alignment.
Section 5.1.3 Open-Label Extension Period	Sentence added to indicate participants switched over to ixekizumab will be treated in separate group.	For accuracy.
Section 5.1.4 Long-Term Extension Period	New section to depict LTE period of study.	For alignment.
Section 5.1.5 Post-Treatment Follow-up Period	LTE post follow up period clarified.	For alignment.
Section 5.3 End of Study Definition	LTE information added.	For alignment.
Section 5.4 Scientific Rationale for Study Design	
 • Added 3-year optionality wording. • Rationale for LTE added. 	For accuracy.
Section 5.5 Justification for Dose	Wording added to clarify LTE dose.	For accuracy.
Section 6.1 Inclusion Criteria	Screening and baseline wording added to Inclusion Criterion #3	For clarification.
Section 6.4 Screen Failures	Wording on ICF/assent form added.	For alignment.
Section 7.1 Treatments Administered	
 • LTE information added to Table RHCG 7.1. • Wording added to Post- Administration Observation. 	For alignment.
Section 7.2 Method of Treatment Assignment	Clarified that all participants who enter LTE will receive ixekizumab.	For clarification.
Section 7.4 Dosage Modification	Clarified dosing during LTE period.	For alignment.

Section # and Name	Description of Change	Brief Rationale
Section 7.7 Concomitant Therapy	
 Clarified use of concomitant therapy in LTE period. Wording on intra-articular joint and bursal corticosteroid injections changed. 	
 For alignment. For clarification.
Section 7.8.1 Study Extensions	Changed wording to include LTE in RHCG study.	For accuracy.
Section 7.8.2 Treatment After Study Completion	Clarified use of adalimumab in LTE period.	For alignment.
Section 8 Discontinuation Criteria	Sentence added to refer to Appendix 3 for discontinuation criteria.	For accuracy.
Section 8.1 Discontinuation from Study Treatment	Paragraph added to clarify permanent discontinuation.	For accuracy.
Section 8.1.1 Permanent Discontinuation from Study Treatment	Updated hepatic parameters for discontinuation and resumption of study drug.	As per updated safety requirements.
Section 8.1.3 Discontinuation of Inadvertently Enrolled Patients	Section removed.	As per new Lilly guidelines.
Section 9.1.3.1 Childhood Health Assessment Questionnaire (CHAQ)	Note added to state the CHAQ will be provided to participants.	For alignment.
Section 9.1.4.5 Morning Joint Stiffness Duration	Note added to state the morning stiffness will be assessed by participants.	For alignment.
Section 9.2.1 Timing and Mechanism, for Collecting Events	Adverse Event collecting events table added.	As per new harmonized template guidelines.
Section 9.3 Treatment Overdose	Updated treatment overdose information.	As per new harmonized template guidelines.
Section 9.4.11.1 Hepatic Safety Monitoring	Hepatic Safety information updated.	As per new safety guidelines.
Section 10.2 Population for Analyses	LTE information added.	For alignment.
Section 10.3.1 General Statistical Considerations	Clarified wording for OLT participants.	For clarification.

Section # and Name	Description of Change	Brief Rationale
Section 10.3.1.2 General Considerations for OLE Period	
 Visit 8 changed to Visit 7. Adalimumab wording added. 	For accuracy.
Section 10.3.1.3 General Considerations for LTE Period	New section added to incorporate general considerations for the LTE period.	For alignment.
Section 10.3.2.1 Participant Disposition	LTE and PTFU wording added.	For accuracy.
Section 10.3.3.2 Secondary Analyses	
 Adjusted Table RHCG.10.2 to incorporate LTE period information. New LTE period Table RHCG.10.5 added. 	For alignment.
Appendix 2. Clinical Laboratory Tests	Updated wording added and outdated wording removed.	As per new harmonized template guidelines.
Appendix 3. Study Governance Considerations	Updated wording added and outdated wording removed.	As per new harmonized template guidelines.
Appendix 4. Hepatic Monitoring Tests for Treatment-Emergent Abnormality	Hepatic Safety information updated.	As per new safety guidelines.
Appendix 5. Adverse Events: Definitions and Procedures for Recording, Evaluating, Follow- up, and Reporting	Updated wording added and outdated wording removed.	As per new harmonized template guidelines.
Appendix 6. Contraceptive Guidance and Collection of Pregnancy Information	Updated contraceptive language.	As per new safety guidelines.
Appendix 7. I1F-MC-RHCG Blood Volume Prioritization Tool	
 Pages updated. Blood volumes updated. 	For accuracy.
Appendix 8 Provisions for Changes in Study Conduct During Exceptional Circumstances	Updated language for LTE period added.	To follow new guidelines.
Appendix 9 Protocol Amendment I1F-MC-RHCG(a)	
 Title removed. Approval date added. 	For alignment.

Section # and Name	Description of Change	Brief Rationale
All Sections	Minor editorial/formatting made throughout, including changing patient wording to participant where applicable.	For accuracy.

Abbreviations: ICF = informed consent form; LTE = long-term extension; O/E = Objectives/Endpoints; OLE = open label extension; OLT = open label treatment; PTFU = post-treatment follow up; SOC = summary of changes.

Amendment [a]: (06-Nov-2020)

Overview

Protocol I1F-MC-RHCG, Multicenter, Open-label, Efficacy, Safety, Tolerability, and Pharmacokinetic Study of Subcutaneous Ixekizumab with Adalimumab Reference Arm, in Children with Juvenile Idiopathic Arthritis Subtypes of Enthesitis-related Arthritis (Including Juvenile-Onset Ankylosing Spondylitis) and Juvenile Psoriatic Arthritis, has been amended.

Overall Rationale for the Amendment:

The overall changes and rationale for changes made to this protocol are described in the following table. Note that minor edits have been made throughout the protocol, which are not captured in the amendment summary table.

This amendment is considered to be substantial based on the criteria set forth in Article 10(a) of Directive 2001/20/EC of the European Parliament and the Council of the European Union.

Amendment Summary for Protocol I1F MC RHCG Amendment (a) 06-Nov-2020

Section #	Description of Change	Brief Rationale
Section 1, Synopsis	Updated status of ixekizumab to approved for plaque psoriasis in adult and pediatric participants, adult psoriatic arthritis, radiographic axial spondyloarthritis (r-axSpA), and non-radiographic axSpA with objective signs of inflammation. Removed Week 16 as a timepoint for PK analysis and relationship between exposure, efficacy, and immunogenicity.	Updated to be consistent with the label. Clarification
Section 2, Schedule of Activities	Extended Screening period from -42 to -14 days to -42 to -7 days.	Correction to standard minimum window for randomization
	For Tanner Stage Scale, added the clarification, “Once the participant reaches the score of 5 on this scale, no further assessments are needed.”	Clarification
	Clarified reading PPD was to be performed locally.	Minor clarification
	Combined HBV DNA row with HBV antibody row.	
	Added the word “site” to administration of study treatment at treatment visits (TV).	
	Deleted TB testing after screening	
	Added urine pregnancy test at every visit starting at Visit 8. Added tests are to be performed locally. Added clarification for testing during instances of delayed menstruation.	In response to Competent Authority request
	Added, “Includes an assessment of rash, serositis, splenomegaly, hepatomegaly, or generalized lymphadenopathy attributable to JIA.” to clinical chemistry.	Clarification
	Added, “V803 is an additional follow-up based on neutrophil count (Section 5.1.4).” as a clarification.	Clarification to be consistent with other ixekizumab studies.
	Added “or ETV” to LV at each follow-up visit.	Clarification

Section #	Description of Change	Brief Rationale
Section 3.2 Background	Updated background information for ixekizumab	Updated to include current study results and indications
Section 4 Objectives and Endpoints	Removed Week 16 as a PK analysis time point Removed Week 16 as an analysis time point for the relationship between exposure, efficacy, and immunogenicity	Clarification Clarification
Section 5.1 Overall Design	Updated screening period and designation of follow-up visits.	For consistency with revisions made to Schedule of Activities
Section 5.1.3 Open-Label Extension Period	Added requirements for participants switching from adalimumab to ixekizumab. A requirement to capture the reasons for switching was also added.	In response to Competent Authority request
Section 5.5 Justification for Dose	Added requirements for participants switching from adalimumab to ixekizumab.	In response to Competent Authority request
Section 6.1 Inclusion Criteria	Added statement, “Participants and their partners of childbearing potential must agree to use contraception for 5 months after the last dose of adalimumab.” to criterion [5].	In response to Competent Authority request
Section 6.2 Exclusion Criteria	Added statement, “Participants with moderate to severe heart failure [NYHA class III/IV] are not eligible for the study.” to criterion [21].	In response to Competent Authority request
Section 7.1 Treatments Administered	Reorganized section by showing the dose level table at the beginning and adding subsections for Dosing and Post-Administration Observation. Added instructions for participants with a body weight of 10.0 kg to 15 kg.	Clarification In response to Competent Authority request
Section 7.7 Concomitant Therapy	Corrected the maximum dose of SSZ to be 3 g/day instead of 3 mg/day. Clarified the conditions for stable use of concomitant medications extend through the OLT period. Added footnote: Dose adjustments may only be made for safety reasons during OLT period (until Week 16).	Typo error Clarification Clarification
Section 8.1.1 Permanent Discontinuation	Revised consultation with Lilly-designated medical monitor to consultation with Lilly Medical.	Clarification on terms

Section #	Description of Change	Brief Rationale
from Study Treatment	Removed criterion of hemoglobin <6.5 g/dL from discontinuation criteria. Corrected typos.	In response to Competent Authority request
Section 8.1.3 Discontinuation of Inadvertently Enrolled Participants	Revised wording	To update to the current harmonized template language
Section 9 Study Assessments and Procedures	Deleted language about 60-day retention period for samples. Removed “Investigators should assess and monitor physical pain and distress at each visit.”	To update to the current harmonized template language Statement did not belong in this section and it was not specific enough for site staff to interpret.
Section 9.2.1.2 Adverse Events of Special Interest	Added sentence, “In the case of suspected IBD, the participant should be referred to a gastroenterologist (preferably pediatric gastroenterologist) for evaluation and management.”	In response to Competent Authority request
Section 9.4 Safety	Added sentence “These events will also be considered as an AE if the event does not result in a diagnosis but is considered clinically significant by the investigator.”	In response to Competent Authority request.
Section 9.4.4 Laboratory Tests	Added mention of the Blood Volume Prioritization Tool as a new appendix.	In response to Competent Authority request
Section 9.4.4.1 Pregnancy Testing	Added section regarding pregnancy testing	To update to the current harmonized template language
Section 10.3.5 Pharmacokinetic/ Pharmacodynamic Analyses	Removed Week 16 as an analysis timepoint	Clarification
Section 10.3.8 Interim Analyses	Removed PK data as an interim analysis	Clarification
Section 10.3.9 Adjudication Committee	Corrected IBD charter to CEC charter	Terminology update
Appendix 2. Clinical Laboratory Tests	Added Neutrophils, juvenile (bands) Added footnote d clarifying urinalysis testing Added clarification for testing during instances of delayed menstruation to serum pregnancy testing footnote. Added clarification about when TB testing is required and add that it is to be performed locally.	Clarification Clarification In response to Competent Authority request Clarification
